1 at	.10 5	4 1	sprominuo minum oi biood minum minimum	

LIST OF IN-TEXT FIGURES

Figure 1.	Nonalcoholic steatohepatitis (NASH) progression [7]	20
Figure 2.	Liver anatomy and lobular zoning [18]	22
Figure 3.	Involvement of the macrophages in the liver damage [15]	24
Figure 4.	Structure of Tc99m-tilmanocept (Lymphoseek®)	25
Figure 5.	Pre-operative SPECT-CT image of a breast cancer patient who had been injected peritumorally with ^{99m} Tc-tilmanocept	26
Figure 6.	IV Administered Tc 99m tilmanocept Localization to RA Joints	32
Figure 7.	Diagrmatic representation of anticipated tessellation	58
LIST OF	APPENDICES	
Appendix 1	Schedule of Events	68
Appendix 2	Sponsor Signatures	70
Appendix 3	Investigator's Signature	71

SYNOPSIS

Study title	An Evaluation of the Safety of Intravenous (IV) Tc 99m Tilmanocept and a Comparison of Localization to Tc 99m Sulfur Colloid by Planar and SPECT/CT Imaging in Subjects with Nonalcoholic Steatohepatitis (NASH) and Healthy Controls (HC)			
Study phase	Phase 1			
Study objective(s)	Primary			
	• Determine the safety and tolerability of Tc 99m tilmanocept in subjects with NASH.			
	Secondary			
	Determine the three dimensional tessellation localization of Tc 99m tilmanocept by planar and SPECT (single photon emission computed tomography)/CT (Computerized x-ray Tomography) imaging in subjects with NASH and asymptomatic controls.			
	• Determine the three dimensional tessellation localization of unfiltered Tc 99m sulfur colloid by planar and SPECT/CT imaging in subjects with NASH and asymptomatic controls.			
	Comparison of liver localization distribution tessellation pattern intensity between Tc 99m tilmanocept and unfiltered Tc 99m sulfur colloid.			
	Exploratory			
	Concordance of intrahepatic localization tessellation discrimination of Tc 99m tilmanocept (intrahepatic disease heterogeneity) by SPECT/CT imaging and elastography			
	Concordance of intrahepatic localization tessellation discrimination of Tc 99m sulfur colloid (intrahepatic disease heterogeneity) by SPECT/CT imaging and elastography			
Duration of treatment	Up to 57 days			
Study drug	Technetium Tc 99m tilmanocept			
	Unfiltered technetium Tc 99m sulfur colloid			

Confidential Page 6 of 71

Dose(s) and Route of administration

Route of Administration: All administrations of Tc 99m tilmanocept and unfiltered Tc 99m sulfur colloid will occur through an intravenous (IV) route of administration. A single syringe will be used for each product and administered as a slow push into the IV. At the completion of each administration, a 10 cc sterile normal saline flush will be administered.

The preferred site of IV placement will be the left or right antecubital vein.

Doses: On Day 0, subjects will receive an on label 8.0 mCi dose of unfiltered Tc 99m sulfur colloid via IV administration. On Day 3, subjects will receive 200 µg of Tc 99m tilmanocept at the specified radiolabel dose of Tc 99m via IV administration.

The first two enrolled subjects will be NASH subjects who will receive an 8.0 mCi radiolabel dose of Tc 99m tilmanocept. A review meeting will be held following completion of the first two subjects to evaluate tilmanocept safety and dose performance.

At the review:

- 1. If it is determined that a lower radiolabel dose of tilmanocept may produce images of better quality, three additional NASH subjects and three HCs will be injected and imaged with 200 µg of 2.5 mCi Tc 99m tilmanocept. After these six subjects have completed the trial, no additional subjects will be enrolled.
- 2. If the review shows no safety signals and acceptable quality of imaging, one additional NASH subject as well as three HCs will be injected and imaged with 200 µg of 8.0 mCi Tc 99m tilmanocept. Once a total of three NASH subjects and three HCs have completed the trial, a second review meeting will be held to compare results from NASH subjects to those of the HCs. If it is determined at the second review meeting that a lower radiolabel dose of tilmanocept may produce additional clinically meaningful results, 3 NASH subjects and 3 HCs will be dosed with 200 µg of 2.5 mCi Tc 99m tilmanocept. If it is determined that additional doses will not provide clinically meaningful results, the trial will be concluded.

Confidential Page 7 of 71

Navidea Biopharmaceuticals, Inc Date: 23 April 2018

Inclusion criteria **ALL SUBJECTS:** 1. The subject has provided written informed consent with HIPAA (Health Information **Portability** Accountability Act) authorization before the initiation of any study-related procedures. 2. The subject is ≥ 18 years of age at the time of consent. 3. The subject has a body mass index (BMI) between 18 and 45. **CONTROL SUBJECTS:** 4. The subject is deemed to be clinically free of any infectious/inflammatory disease(s) for at least 4 weeks prior to the consent date. 5. The subject has not taken any antibiotics for at least 4 weeks prior to the consent date. NASH SUBJECTS: 4. The subject has biopsy-confirmed NASH within 12 months prior to enrollment. 5. The subject has a Nonalcoholic Fatty Liver Disease (NAFLD) Activity Score (NAS) of ≥ 4 , with a score of at least 1 for each steatosis, lobular inflammation, and hepatocyte ballooning. 6. The subject has fibrosis staging of F3-F4. ALL SUBJECTS: **Exclusion criteria** 1. The subject is pregnant or lactating. 2. The subject size or weight is not compatible with imaging per the investigator. 3. The subject has received radiation therapy or chemotherapy or has a previous diagnosis of cancer other than basal cell carcinoma. 4. The subject has renal insufficiency as demonstrated by a glomerular filtration rate (GFR) < 60 mL/min. 5. The subject has a chronic or persistent infection or has any condition that would, in the opinion of the examining physician, preclude their participation. 6. The subject has a known allergy to or has had an adverse reaction to dextran exposure. 7. The subject has received an investigational product within 30 days prior to the Tc 99m sulfur colloid administration.

Confidential Page 8 of 71

Navidea Biopharmaceuticals, Inc Date: 23 April 2018

- 8. The subject has received any radiopharmaceutical within 7 days prior to the administration of Tc 99m sulfur colloid.
- 9. The subject is HIV positive.
- 10. The subject has a history of alcohol abuse or currently consumes alcohol in excess of 3 drinks/day for men or 2 drinks/day for women.
- 11. The subject has hepatitis B or C.

CONTROL SUBJECTS:

- 12. The subject has hepatic insufficiency as demonstrated by ALT (alanine aminotransferase [SGPT]) or AST (aspartate aminotransferase [SGOT]) greater than two times the upper limit of normal (ULN).
- 13. The subject has been diagnosed with NASH, NAFLD, or other chronic liver disease.
- 14. The subject has been diagnosed with metabolic syndrome or Type I or II diabetes.

NASH SUBJECTS:

- 12. The subject has any chronic liver disease aside from NASH/NAFLD.
- 13. The subject has uncontrolled diabetes as indicated by an A1c >9% within the 3 months prior to enrollment.

Study design

Prospective, open-label, multicenter, safety, comparative study of injected Tc 99m tilmanocept and unfiltered Tc 99m sulfur colloid in the detection of and assessment of three dimensional tessellation localization to the liver in subjects with and without moderate to severe NASH by planar and SPECT/CT imaging.

On Day 0, subjects will receive IV administration of 8.0 mCi of unfiltered Tc 99m sulfur colloid. Subjects will have planar imaging of the liver followed by SPECT/CT scanning of the abdomen, liver, and spleen at 20 minutes \pm 5 minutes postadministration.

On Day 3, subjects will receive IV administration of 200 μg of tilmanocept at the specified radiolabeled dose of Tc 99m. Subjects will have planar imaging of the liver followed by SPECT/CT scanning of the abdomen, liver, and spleen at three specified time points post-administration: 20 minutes \pm 5 minutes, 75 minutes \pm 15 minutes and 180 minutes \pm 15 minutes.

Confidential Page 9 of 71

Methodology

The study includes: screening, enrollment, pre- and post-injection assessments, administration of unfiltered Tc 99m sulfur colloid, administration of Tc 99m tilmanocept, imaging and follow-up.

Visit 1, Screening (Day -45 to Day -1): The screening visit will include informed consent, review of study eligibility, demography, collection of medical history including medications, vital signs, ECG (electrocardiogram), physical exam including height and weight, clinical labs, urinalysis, a serum pregnancy test for subjects of childbearing potential, and a transient elastography. Adverse event monitoring will begin from Visit 1 Screening and continue through subject completion of the trial.

Visit 2, Day 0:

Pre-Tc 99m Sulfur Colloid Administration:

- Before Administration (Day 0)
 - Urine pregnancy test will be performed for subjects of childbearing potential
 - Assessment of adverse events
 - Concomitant medication review
 - o Vital Signs within 15 minutes prior to administration

Tc 99m Sulfur Colloid Administration : Subjects will receive the on label 8.0 mCi dose.

Post-Tc 99m Sulfur Colloid Administration:

- 20 ± 5 Minutes Post-Administration:
 - Assessment of adverse events
 - Vital Signs
 - Planar imaging of the liver/spleen followed by SPECT/CT of the liver/spleen and abdomen

Visit 3, Day 3:

Pre-Tc 99m Tilmanocept Administration:

- Before administration (Day 3)
 - Urine pregnancy test will be performed for subjects of childbearing potential
 - Assessment of adverse events

Confidential Page 10 of 71

	Concomitant medication review			
	o Vital Signs - within 15 minutes			
	administration	 		
	Tc 99m Tilmanocept Administration: Subjects will receive the open label 200 μg at the specified radiolabeled dose.			
	Post-Tc 99m Tilmanocept	Administration:		
	• 20 ± 5 Minutes Post-Administration:			
	o Assessment o	f adverse events		
	o ECG (comple	eted before vital signs)		
	 Vital Signs 			
		ng of the liver/spleen followed by f the liver/spleen and abdomen		
	• 75 ± 15 Minutes Pos	t-Administration:		
	o Assessment o	f adverse events		
	 Planar imaging of the liver/spleen followed by SPECT/CT of the liver/spleen and abdomen 			
	• 180 ± 15 Minutes Post-Administration:			
	 Assessment of adverse events 			
	 Planar imaging of the liver/spleen followed by SPECT/CT of the liver/spleen and abdomen 			
	After Completion of All Imaging:			
	o Blood draw testing	for hematology and chemistry		
	 Urine collecti 	on for urinalysis		
	Day 8 ± 3 :			
	Safety Follow-Up Telephor of Tc 99m Tilmanocept:	ne Call 5 ± 3 Days Post-Injection		
	Concomitant medica	tion review		
	Assessment of adverse events			
Planned study dates	Planned study dates Start of study recruitment / November 2018			
	End of Study/September 2018			
Planned number of study centers	Approximately 1-3 centers in the United States			
Number of subjects	Up to 12 evaluable subjects may be enrolled.			
.	J,			

Confidential Page 11 of 71

Primary Endpoint	Proportion of subjects experiencing a noxious pharmacologic activity/adverse drug reaction (ADR)	
Secondary Endpoints	Determine the three dimensional tessellation localization of Tc 99m tilmanocept by planar and SPECT/CT imaging in subjects with NASH and asymptomatic controls.	
	Determine the three dimensional tessellation localization of unfiltered Tc 99m sulfur colloid by planar and SPECT/CT imaging in subjects with NASH and asymptomatic controls.	
	Comparison of liver localization distribution tessellation pattern intensities between Tc 99m tilmanocept and unfiltered Tc 99m sulfur colloid	
Exploratory Endoints	*	
	Concordance of intrahepatic localization tessellation discrimination of Tc 99m sulfur colloid (intrahepatic disease heterogeneity) by SPECT/CT imaging and elastography	
Data Analyses	The following analysis population will be defined for the study:	
	• Intent-to-Diagnose (ITD) Population - Subjects who are enrolled in the study, administered Tc 99m tilmanocept and unfiltered Tc 99m sulfur colloid, and are imaged will be included in the ITD analysis population.	
	• Safety Population – All patients who are enrolled and administered Tc 99m tilmanocept and unfiltered Tc 99m sulfur colloid in the study will be included in the safety population.	
	All safety data analyses will be conducted on the safety population. All efficacy data analyses will be conducted on the ITD population.	
	The number and percentage of subjects experiencing noxious pharmacologic activity or ADRs will be tabulated by subject type, Tc 99m tilmanocept dose group (if applicable), and overall.	

Confidential Page 12 of 71

Tc 99m tilmanocept Clinical Study Protocol Number: NAV3-30

> Per subject localization rates and percentage will be calculated by time point, by subject type, Tc 99m tilmanocept dose group (if applicable), and overall.

> Localization intensities (tessellation) will be summarized by descriptive statistics (mean, median, standard deviation, minimum, maximum and range) at each time point. All results will be compared to statistics computed on the control group at each time point.

Confidential Page 13 of 71

Clinical Study Protocol Number: NAV3-30

LIST OF ABBREVIATIONS AND DEFINITIONS OF TERMS

ADR adverse drug reaction

AE adverse event

ALT alanine aminotransferase (SGPT)

AST aspartate aminotransferase (SGOT)

[figure not shown]
BMI body mass index

BUN blood urea nitrogen

CCL2 CC-chemokine ligand 2

CCR2 CC-chemokine receptor 2

CD206 Mannose-binding receptor (Ca2+-binding lectin)

CO₂ carbon dioxide

CRA clinical research associate

CRF case report form

CRO contract research organization

CSF1 Macrophage colony-stimulating factor 1

CSF1R CSF1 receptor

CT X-ray computed tomography

CX3CR1 CX3C-chemokine receptor 1

CXCL CXC-chemokine ligand

CXCR CXC-chemokine receptor

Clinical Study Protocol Number: NAV3-30

Cy3 cyanine dyes fluoresce orange (~550 nm excitation, ~570 nm

emission)

$$\begin{array}{c|c} & 1 & 3 \\ & & 1 \\ \hline & 1 \\ & & R \\ & & Cy3 \end{array}$$

DAMPs Damage-associated molecular patterns

DICOM Digital Imaging Communications in Medicine

DTPA diethylene triamine pentaacetic acid

ECG electrocardiogram

EU European Union

FASL FAS ligand

FDA Food and Drug Administration

FNR false negative rate

GCP Good Clinical Practice

GFR Glomerular Filtration Rate

HC Healthy controls

HCT hematocrit

Hgb hemoglobin

HIPAA Health Information Portability and Accountability Act

ICF informed consent form

ICH International Conference on Harmonization

%ID_{SN} percentage of Injected Dose in the Sentinel Node

IL-10 Interleukin-10

IL-1β Interleukin-1β

IL-6 Interleukin-6

ILM intraoperative lymphatic mapping

IRB Institutional Review Board

ISF investigator site file

Tc 99m tilmanocept

Clinical Study Protocol Number: NAV3-30

ITD intent-to-diagnose population

IV intravenous

K_D Dissociation constant

kDa kiloDalton (molecular weight designation)

LN lymph node

LSEC Liver sinusoidal endothelial cell

LY6C Lymphocyte antigen 6 complex

M1 Macrophage 1

M2 Macrophage 2

mCi milliCurie (37x10⁶ becquerels; 37megabecquerels)

MedDRA Medical Dictionary for Regulatory Activities

MoMFs Monocyte-derived macrophages

MRI Magnetic Resonance Imaging

MRS Magnetic Resonance Spectroscopy

MSR1 Macrophage scavenger receptor 1

MTD maximum tolerated dose

NAFLD nonalcoholic fatty liver disease

NAS nonalcoholic fatty liver disease activity score

NASH nonalcoholic steatohepatitis

NHANES National Health and Nutrition Examination Survey

NO Nitric oxide

NOAEL no-observed adverse-effect level

PGE2 Prostaglandin E2

PI principal investigator

RA Rheumatoid Arthritis

RBC red blood cells

ROS Reactive oxygen species

SAE serious adverse event

SAP statistical analysis plan

Confidential Page 16 of 71

Clinical Study Protocol Number: NAV3-30 Date: 23 April 2018

SC Subcutaneous

SCC squamous cell carcinoma

SLN sentinel lymph node

SLNB sentinel lymph node biopsy

SPECT single photon emission computed tomography

SUSARs Suspected, Unexpected, Serious Adverse Reactions

Tc 99m technetium-99m metastable isotope; γ -emitting (t½ = 6.02 h)

TcSC Tc 99m Sulfur Colloid

Tessellation Three dimensional differntial localization or heterogeneity of intrahepatic

signal

TGF-β Transforming Growth Factor-β

Tilmanocept DTPA Mannosyl Dextran (the US Adopted Name for the drug substance

of Lymphoseek®)

TMF trial master file

TNF Tumour necrosis factor

ULN upper limit of normal

US United States

VEGFA Vascular endothelial growth factor A

VBD vital blue dye

WBC white blood cell

wt weight

Confidential Page 17 of 71

STUDY ADMINISTRATIVE STRUCTURE

The principal investigator (PI) must sign the protocol signature sheet before study participant recruitment may start. Likewise, all protocol amendments must be signed and dated by the PI before coming into effect.

The name and address of the participating center, the investigators, and all required signature documents will be maintained in the trial master file (TMF).

In addition to the PI, there are additional onsite roles that may be performed by other sub-investigators:

- Subject referral to the study
- Review of subject eligibility and medical records
- Clinical evaluations
- Safety assessments
- Injection and imaging
- On-site image analysis

Study personnel not listed in this section are identified in a separate personnel list. This list will be updated as needed. The list of personnel will be available in the center's investigator site file (ISF).

Confidential Page 18 of 71

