NASH is an inflammatory syndrome in which immune cells infiltrate into and accumulate in liver tissue [14, 15]. Numerous among these immune cells are macrophages. There are two types of macrophages in the liver. The first type consists of Kupffer cells (aka stellate macrophages) that reside within the endothelial lining of blood vessels in the liver. The second type of macrophages in the liver consists of macrophages differentiated from bone marrow derived monocytes that have infiltrated into the liver and developed into activated macrophages in response to inflammatory signals originating in the liver [14]. It is hypothesized that Tc 99m tilmanocept, through its affinity to CD206, will bind to and accumulate in both types of liver macrophages permitting the degree and anatomical distribution of Tc 99m tilmanocept localization to be used as an indicator of the presence and intensity of NASH related hepatic inflammation. In addition, NASH results in the development of fibrotic lesions in the liver, basically scars resulting from resolved inflammation. These fibrotic lesions are depleted of macrophages, thus are expected to be regions of much reduced Tc 99m tilmanocept localization relative to regions where NASH related inflammation is ongoing [1, 16, 17]. In both cases of either increased Tc 99m tilmanocept localization due to active NASH mediated inflammation or decreased Tc 99m tilmanocept localization due to macrophage depletion due to fibrotic resolution of NASH mediated inflammation, the degree and distribution of Tc 99m tilmanocept localization is expected to significantly differ in NASH involved livers relative to the degree and distribution of Tc 99m tilmanocept localization

observed in livers which are not involved in NASH inflammation. This clinical study will provide a preliminary evaluation of the degree and distribution of Tc 99m tilmanocept localization in healthy livers and those involved in NASH inflammation. If this and follow on studies are successful in establishing that Tc 99m tilmanocept enabled imaging can identify areas of NASH involvement or resolution, then it may be possible to develop Tc 99m tilmanocept as a NASH imaging agent that can assist physicians to non-invasively diagnose and monitor NASH, thus satisfying the need for a non-invasive means to diagnose and assess NASH.

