9.5.3 Analysis of Efficacy Variables

Co-location of tilmanocept and sulfur colloid intrahepatic tessellation localization (Figure 7) will be assessed through frequency tables derived by creating virtual slices of the liver.. These scans will be false-colored and overlaid, matching landmarks (e.g. large blood vessels) for image registration. The resulting voxel colors will be classified as binding tilamanocept, binding sulfur colloid, or binding both. No formal hypothesis tests are planned. Frequency tables will created for individual subjects and overall.

The voxel radiation intensities will be used to create non-parametric density estimates of ^{99m}Tc gamma radiation intensities for both Tc 99m tilmanocept and Tc 99m sulfur colloid. Density estimates will be created for both individual subjects and for NASH subjects and healthy controls pooled separately.

[figure not shown]

Figure 7. Diagrmatic representation of anticipated tessellation

Complete analyses and details will be described in the Statistical Analysis Plan (SAP) for the study.

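### The stated NASH-control summaries may miss or misstate within-liver heterogeneity: no per-subject heterogeneity measure is named, and the pooled voxel densities are not split by dose

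*Combined protocol and SAP*

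**What the plan says.** The list of abbreviations defines tessellation as "Three dimensional differntial localization or heterogeneity of intrahepatic" signal, and all three secondary objectives (Section 2.2) are framed in that term.

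Section 1.1 gives the biology. Tilmanocept "will bind to and accumulate in both types of liver macrophages", meaning resident Kupffer cells and infiltrating macrophages. Signal may move either way in NASH: "In both cases of either increased Tc 99m tilmanocept localization due to active NASH mediated inflammation or decreased Tc 99m tilmanocept localization" where fibrosis has depleted macrophages. Section 1.3 adds that Kupffer cells take up sulfur colloid whatever their activation state.

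The synopsis (Data Analyses) plans three things:
- "Per subject localization rates and percentage will be calculated by time point, by subject type", and also by dose group if applicable and overall;
- "Localization intensities (tessellation) will be summarized by descriptive statistics (mean, median, standard deviation, minimum, maximum and range) at each time point";
- a comparison of these findings with the controls' values, time point by time point.

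Section 9.5.3 lists different analyses. In the overlay of the two scans, "The resulting voxel colors will be classified as binding tilamanocept, binding sulfur colloid, or binding both", with frequency tables per subject and overall. For voxel intensities, "Density estimates will be created for both individual subjects and for NASH subjects and healthy controls pooled separately". It plans no formal tests and leaves full details to the SAP. The combined document as supplied contains no further SAP analysis text.

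**The concern.** The quantity of interest is spread within a liver, but no section names a per-subject number that measures it. The synopsis tabulates a rate and a set of intensity statistics whose unit is not stated. The only voxel-level contrast between NASH and controls is a pair of pooled density curves, with no stated split by dose group and no stated normalisation.

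With at most six subjects per group and no tests, these descriptive summaries are the result. If they are blunt, a real pattern could be reported as no difference from controls. If pooling mixes doses, a dose artefact could be reported as heterogeneity. Without a measure fixed in advance, one could also be chosen after the images have been seen.

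**Working it through.** The plan offers no figure to reproduce. Section 9.4 states N=12 without an effect size, SD, alpha or power. The check is therefore of what each summary can show. Effect sizes, liver fractions and voxel noise below are assumptions, because the documents give none.

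**1. Localization rate.** Both agents are expected in resident Kupffer cells, which healthy livers also have. If localization is scored yes/no per subject, the expected rate is about 100% in both groups and the difference about 0, whatever the pattern. The exact 95% lower limit for n out of n is 0.025^(1/n): 29.2% for 3/3 and 54.1% for 6/6.

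**2. Whole-liver mean.** Inclusion criteria 5 and 6 for NASH require a lobular inflammation score of at least 1 and fibrosis F3-F4, so both opposing processes are present in every NASH liver. Set healthy intensity to 1 with voxel CV 0.15. Let a fraction f be inflamed with gain g, and a fraction h fibrotic with loss l.
- Mean = 1 + fg − hl
- Variance = 0.15² + fg² + hl² − (fg − hl)²

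| f, g, h, l | Mean | SD | SD relative to healthy (0.15) |
|---|---|---|---|
| 0.3, 0.5, 0.3, 0.5 | 1.00 | √0.1725 = 0.415 | 2.8 |
| 0.2, 0.2, 0.2, 0.2 | 1.00 | √0.0385 = 0.196 | 1.3 |
| 0.1, 0.5, 0.4, 0.8 | 0.73 | √0.2306 = 0.480 | 3.2 |

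The third row shows no cancellation. A grid of 500 combinations (f and h 0.1 to 0.5, g 0.2 to 1.0, l 0.2 to 0.8) gave mean changes from −38% to +48%. The mean was within 5% of normal in 29% and within 10% in 52%. Where it was within 5%, the SD ratio was at least 1.16 (median 2.2).

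**3. SD and range in the synopsis.** Taken across voxels within a liver, they register this pattern. Taken across subjects, they do not: if every NASH liver followed row 1, the pattern would add 0 to the between-subject SD of liver means, although each liver has SD 0.415. The synopsis does not say which is meant. Section 9.5.4 uses the same list of statistics for vital signs, ECG and laboratory values, where it runs across subjects.

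**4. Pooled densities.** Under option 1 of Section 5.2, NASH would comprise two subjects at 8.0 mCi and three at 2.5 mCi, and all three controls would be at 2.5 mCi. Assume intensity proportional to activity, equal voxel counts per subject and no normalisation.
- NASH mean = (2×8.0 + 3×2.5)/5 = 4.7
- NASH variance = (2×3.3² + 3×2.2²)/5 = 7.26, so SD = 2.69
- CV from dose alone = 2.69/4.7 = 0.57, against 0 in controls

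Pooled CV² = (1 + dose CV²)(1 + within-liver CV²) − 1. With no true heterogeneity in either group (within-liver CV 0.15), NASH gives √(1.3287×1.0225 − 1) = 0.60 against 0.15 in controls, a fourfold contrast produced by dose.

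Option 2 with its second stage has three per group at each activity: mean 5.25, SD 2.75, dose CV² = 0.274 in both groups. Row 1 would then give √(1.2744×1.1722 − 1) = 0.70 against √(1.2744×1.0225 − 1) = 0.55. That is a ratio of 1.3, where the within-liver ratio is 2.8.

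**5. Per-subject outputs in Section 9.5.3.** An individual density would show row 1 as a widened curve (1st to 99th percentile 0.23 to 1.78, against 0.65 to 1.35 in healthy liver). No number is taken from it for comparison with controls. The co-location tables are not stated by subject type and have no class for voxels binding neither agent, which is where depleted fibrotic tissue would fall.

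**The case against.** A reader might infer that the plan cannot register the NASH pattern at all. The documents do not support that. The synopsis lists SD, minimum, maximum and range as well as the mean, and an SD across voxels divided by the mean is exactly a heterogeneity index. Section 9.5.3 provides per-subject voxel densities, in which a widened or two-peaked distribution would be visible. Cancellation in the mean is exact only if fg = hl, and the documents give no magnitudes; in 71% of the assumed combinations the mean moved by more than 5%. Saturation of the rate depends on a yes/no reading, and localization is not defined. A percentage of voxels per subject need not be near 100%. Further detail is deferred to the SAP, so its absence there cannot be shown. All of this stands, and it limits the point to *may miss or misstate*.

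Two objections bear on the remedy. First, SD/mean discards location just as the density does. That is true, so it belongs beside the spatial tables and does not replace them. Second, a tilmanocept-minus-colloid difference in the index is confounded when activities differ. With count-limited noise, equal uptake and equal scan time, going from 8.0 to 2.5 mCi multiplies noise by √(8.0/2.5) = 1.79, so 10% noise becomes about 18%, a spurious difference of 0.08 in a uniform liver. That also stands and restricts where the difference should be reported.

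The deferral to the SAP does not remove the point: the synopsis and Section 9.5.3 list different analyses, and the text supplied does not reconcile them.

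**Conclusion.** The point holds in a limited form. The stated NASH-control summaries may fail to register, or may misstate, the hypothesised heterogeneity. The rate is probably uninformative if scored yes/no. The mean can be blunted: within 5% of normal in 29% of assumed scenarios, with within-liver SD then at least 1.16 times healthy. The synopsis SD and range help only if taken across voxels. The pooled densities combine within-liver spread with between-subject and dose differences. Dose alone could create a fourfold contrast under option 1, or shrink a 2.8-fold contrast to 1.3-fold under the two-stage form of option 2.

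These sizes rest on the assumed fractions, gains, losses and noise, and on intensity scaling with activity without normalisation. The direction of each effect rests on the protocol's own biology and dosing paths. The trial is small, descriptive and has safety as its primary objective, so this is a low-cost improvement and not a flaw that undermines the study.

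**What to change.** In the SAP, with matching wording in the synopsis and Section 9.5.3:

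1. Add a per-subject index: SD/mean of voxel intensity inside the CT-defined liver volume, for each agent and time point, tabulated by subject type within tilmanocept dose group. Keep the existing rate, descriptive statistics, densities and co-location tables beside it.
2. State that the SD and range for tessellation are taken across voxels within a liver.
3. Split the pooled densities by dose group, or normalise each subject's intensities before pooling. Section 5.2 allows ±20% on the radiolabel dose, so normalisation also helps within a dose group.
4. Report the tilmanocept-minus-colloid difference in the index only where both activities are 8.0 mCi, and only at 20 minutes, the sole colloid time point. Under option 1 this would cover two NASH subjects and no controls.

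The cost is SAP wording and modest programming on images already acquired, with no added scans, visits or subjects. The downside is that the index depends on image noise, camera and reconstruction. Section 8.2 lets sites follow their own camera parameters, so the index is comparable only within dose group and should be read with site in mind. It also discards location and only complements the spatial tables.
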